## 3.0 Intervention to be studied

Subjects will be screened for likely inclusion during the summer months. Baseline demographics, medical comorbidities, and URI symptoms will be assessed. Informed consent will be completed.

The fall URI season typically runs through September and October (Turner R et al). Towards the end of screening, all subjects will be randomized 2:1 to active use of Sinusonic (128Hz) for 1 minute 3 times daily or an identical “placebo” device that emits a frequency of 1,000 Hz and has the ball valve modified to eliminate positive expiratory pressure. Devices will be shipped to home addresses via overnight mail. On September 1, 2020 all subjects will begin daily use of their assigned device. Subjects will remain blinded as to treatment arm until study completion.

Subjects will be asked to complete a brief daily questionnaire on URI symptoms and whether or not they feel as if they have a “cold”. Previously validated questions for viral URI studies are rating 8 items on a likert scale from 0 (no symptoms) to 3 (severe symptoms) (Jackson GG, et al). The 8 symptoms are: sneezing, runny nose, nasal obstruction, sore throat, cough, headache, malaise, and chilliness. A Total Symptom Score (TSS) will be the sum of each symptom to provide a daily score ranging from 0 to 24. Prior studies have defined the common cold as present when:

- 1)  $TSS \geq 14$  PLUS moderate or severe nasal discharge x 3 days OR patient subjective impression they have a cold OR

2) TSS < 14 AND moderate or severe nasal discharge x 3 days AND subjective impression they have a cold

Answers will be uploaded to secure REDCAP database. The study duration is 8 weeks. At the end of the study, subjects will be asked questions regarding device safety and tolerability.

Our primary outcome will be absolute number of URIs experienced during the 8 week study period. Secondary outcomes will be time to first URI, duration and symptom severity of viral URIs. These metrics will allow us to determine if Sinusonic decreases the frequency of URIs, as well as potentially shortening the duration or decreasing the severity of URIs.

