#### **5.0 Number of Subjects**

Prior research reports (Turner etal) using identical outcome measures and studying community acquired URIs in the fall season report that approximately 60% of subjects suffered from a viral URI (range 48% to 75% in each arm). We are planning to include 300 subjects (200 active device, 100 sham device). If we conservatively assume that only 50% of sham device subjects get an URI, we will be powered to detect a decrease to 33%.

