## 10.0 Data Management

All analyses and graphs will be performed with SPSS 24.0, Sample Power 3.0, and Sigma Plot 10.0 (SPSS, Chicago, IL.). Disease information and demographic variables, such as age, gender, race, and VAS scores will be summarized using frequencies, means, and standard deviation as appropriate. Our primary outcome metric is number of viral URIs as defined above. Secondary outcome metrics include average duration of URIs and severity of symptoms (as measured by TSS) of URIs. Categorical variables will be compared using Chi Square or McNemar's test. Continuous variables will be compared using One-Way ANOVA with repeated measures follow by post-hoc analysis. Data regarding safety and patient satisfaction will be summarized for each time point. A p-value  $\leq 0.05$  will be considered statistically significant. Due to the exploratory nature of this study, no p-value correction (ie Bonferroni) will be applied.

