## **12. Withdrawal**

At any point during the study, a subject may withdraw from the study. The subject may refuse to take part in or stop taking part in this study at any time. The subject will be instructed to call the investigator in charge of this study if they decide to do this. Their decision not to take part in the study will not affect their current or future medical care or any benefits to which they are entitled. If they wish to withdraw, they will be provided contact details for the study team to initiate their withdrawal.

Early termination from the study is also subject to the PI's discretion. Subject will no longer be in the study and data will no longer be collected. The reasons for this withdrawal could be due to study non-compliance or if the subject no longer meets eligibility requirements. A member of the study team will notify the study participant if they will no longer be participating in the study.

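### Time to first URI has no method for censored data, URI diaries stop when the investigator removes a subject, and no test is assigned to the primary URI count

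*Combined protocol and SAP*

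**What the plan says.** Section 3.0 sets the outcomes: "Our primary outcome will be absolute number of URIs experienced during the 8 week study period", and "Secondary outcomes will be time to first URI, duration and symptom severity of viral URIs". Section 10.0 repeats the primary: "Our primary outcome metric is number of viral URIs as defined above". Its list of secondary outcomes is shorter: "Secondary outcome metrics include average duration of URIs and severity of symptoms (as measured by TSS) of URIs". Time to first URI does not appear there.

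Section 10.0 gives tests by variable type and links none of them to a named outcome. Categorical data get chi-square or McNemar. The other sentence reads: "Continuous variables will be compared using One-Way ANOVA with repeated measures follow by post-hoc analysis". No Kaplan-Meier, log-rank, Cox or count model appears anywhere.

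Section 5.0 justifies 200 active and 100 sham subjects on the share with any URI: "If we conservatively assume that only 50% of sham device subjects get an URI, we will be powered to detect a decrease to 33" per cent. It states neither the power nor the sidedness.

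Section 12 lets the investigator end participation early, with non-compliance among the possible reasons. It then says: "Subject will no longer be in the study and data will no longer be collected". Sections 11.0 and 18.0 keep SAE reporting open until 30 days after last use, so what is lost is chiefly the URI diary. No section gives an analysis population, a missing-data rule, a removal rate or a denominator of days observed.

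**The concern.** There are three gaps, the third smaller than the others.

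1. A subject with no URI by the end of follow-up has a censored time, not a measured one. With only ANOVA and chi-square listed, the analyst must either invent a value for most of the sample or drop those subjects.

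2. Removal for non-compliance happens after randomisation and may depend on what it is like to use the assigned device. Once the diary stops, the subject has fewer days in which to record a URI. The plan does not say whether such a subject is kept with a shortened count or left out. The first can bias the comparison if removal differs by arm, and the second can if removal is related to URI risk.

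3. The declared primary is a count, the powered outcome is a proportion, and the count has no named test. Two of the listed methods (McNemar and repeated-measures ANOVA) are within-subject methods and do not fit one total per subject in two independent arms.

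**Working it through.** **Inputs.** From Section 5.0: 100 sham, 200 active; 50% and 33% with any URI. From Section 3.0: 8 weeks, or 56 days. From Section 10.0: significance at 0.05. Assumed: two-sided testing, constant URI hazards, and all removal rates. The Section 9.1 table runs from day 12 to day 60, which is 48 days rather than 56. As 50% and 33% are totals over the window, the time-to-event and count comparisons scale with either length.

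**The plan's own figure.** Pooled proportion (50 + 66)/300 = 0.3867. Null SE = √(0.3867 × 0.6133 × (1/100 + 1/200)) = 0.0596. Alternative SE = √(0.25/100 + 0.33 × 0.67/200) = 0.0600. Power = Φ[(0.17 − 1.96 × 0.0596)/0.0600] = Φ(0.884) = 81.2%. At 80% power the formula needs 98 sham and 294 in total. The 300 therefore reproduces for any URI.

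**Time to first URI.** Expected URI-free: 100 × 0.50 + 200 × 0.67 = 50 + 134 = 184, leaving 116 events. Hazard ratio = ln 0.67 / ln 0.50 = 0.578. The Schoenfeld approximation gives Φ(√(116 × 1/3 × 2/3) × 0.549 − 1.96) = Φ(0.825) = 79.5%. Simulated power:

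| Method | Power |
|---|---|
| Log-rank | 83% |
| ANOVA, URI-free subjects set to day 56 | 74% |
| ANOVA, infected subjects only | 7% |

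All three keep type I error at about 5%, so the loss is of power.

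**Removal, no true effect, unrelated to risk, shortened counts kept.** If removal times are uniform, a removed subject is observed for half the window on average. The expected count ratio is then (1 − active rate/2)/(1 − sham rate/2): 0.90/0.95 = 0.95 at 20%/10%, and 0.85/0.95 = 0.89 at 30%/10%. In simulation, with each removal time rounded up to a whole diary day:

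| Active/sham removal | Count ratio | False positives, count | False positives, any URI |
|---|---|---|---|
| 10%/10% | 1.00 | 5.0% | 5.6% |
| 10%/5% | 0.98 | 5.4% | 5.9% |
| 20%/10% | 0.95 | 6.7% | 7.0% |
| 30%/10% | 0.90 | 11.1% | 11.9% |

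An observation-time offset returns the ratio to 1.00 with 5.0–5.1% false positives. Completers only also gives 1.00 (4.7–5.1%) when removal is unrelated to risk.

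**Removal related to risk.** Suppose half the subjects have twice the URI rate and removal is 10%, except 50% in high-risk active subjects. The completers' ratio is 0.91 (9.2% false positives) and the offset ratio 0.97. The offset reduces this bias but does not remove it.

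**Equal removal of 20%, planned effect.** Completers' power is 84% for the count and 72% for any URI; with the offset, count power is 87%.

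**Power for the count.** Poisson means matching 50% and 33% are −ln 0.50 = 0.693 and −ln 0.67 = 0.400. With complete follow-up, between-arm ANOVA and robust Poisson each have about 91% power. Power is 89%, 87% and 86% if a new URI cannot start for 7, 14 or 21 days, and 82% if nobody has a second URI. Under overdispersion the answer depends on what is held fixed. With the means fixed and negative-binomial dispersion 1 or 2, power is about 76% or 63%, but the shares infected then fall below the Section 5.0 rates. With 50% and 33% fixed, power is 94–99%.

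**The case against.** The strongest reply is that the plan is coherent on its main point. Sections 3.0 and 10.0 agree that the count is primary. A between-arm ANOVA on complete counts is valid (5.1% type I error). The any-URI calculation is the more cautious basis for sample size in every Poisson or limited-repeat case above. That stands. A reader might infer that 300 subjects are too few, or that the ANOVA sentence is itself an error; the documents support neither. The within-subject methods could be meant for daily symptom scores or for the 4- and 8-week measures in Section 6.0.

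A reader might also infer that the outcome can be picked once results are known. Reporting whichever of the count and any-URI tests is significant would give 7.9% false positives under Poisson counts, but no section proposes that. What is open is the test for the count.

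On removal, the documents give no reason to expect more in the active arm: subjects are blinded, and Section 13.0 cites mild discomfort in 2.5–5%. At 10%/5% the inflation is slight. The bias also needs shortened counts to be kept, or removal related to risk in a completers' analysis. So a reader who concludes that the trial is biased goes too far. Still, Section 12 states the rule, Section 18.0 has compliance checked by weekly calls, and no analysis rule guards against the consequence.

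Finally, the trial is a pilot and described as exploratory. That explains the absence of multiplicity correction. It does not supply a method for a listed secondary outcome or a test for a declared primary.

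**Conclusion.** The point holds and should be fixed.

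- **Time to first URI.** The omission is plain on the page. At the plan's own rates and constant hazards it costs about 9 points of power (83% against 74%) if URI-free subjects are set to day 56. Nearly all power goes only if they are dropped, which the plan does not specify.
- **Removal.** The data-collection rule and the lack of any allowance for days observed are certain; the harm is conditional. Equal removal unrelated to risk costs power only. Ratios of 0.95 and 0.90 arise only under assumed removal of 20%/10% and 30%/10% with shortened counts kept.
- **Powered outcome and declared outcome.** This is a lesser matter of clarification. Count power is about 82–91% under Poisson or limited-repeat assumptions. It depends on overdispersion, which the documents do not give, so the sample size is neither shown to be inadequate nor justified for the count.

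**What to change.** 1. **Primary.** Analyse the number of URIs by assigned arm with Poisson regression and robust standard errors. Use as offset the log of days under observation, from first diary to last diary or day 56, in all randomised subjects with diary follow-up. Report by arm those with none; Section 9.1 puts randomisation on day 1 and study start at 12 days, so there may be some. State when a new episode counts as a second URI, because Section 3.0 has no such rule and a count cannot be reproduced without one. State how intermittently missed diary days are handled, with completed-diary days as offset in a sensitivity analysis; the simulations above do not cover intermittent gaps. Name the any-URI chi-square that Section 5.0 powers as the supporting analysis.
2. **Time to first URI.** Add Kaplan-Meier, log-rank and Cox to Section 10.0, censored at last diary.
3. **Section 12.** Continue the existing electronic diary after device discontinuation or investigator removal unless the subject withdraws consent, with matching consent wording. Leave the grounds for removal unchanged.
4. **Sensitivity.** Give unobserved active-arm days 1, 1.5 and 2 times the observed sham rate, and unobserved sham days 1 times. With 10% of active days unobserved, a ratio of 0.578 becomes 0.9 × 0.578 + 0.1 × k: 0.62, 0.67 and 0.72. Adjustment for exposure variables already collected (contact with young children, frequent flying) is optional and removes only the part of risk-related removal that they explain.

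**Cost.** SAP wording, a protocol sentence, a little more analysis, continued diary prompts and possibly revised consent wording; no new visits or forms. Continued diaries guard against bias rather than add power: if any device effect ends when use stops, count power is 87% at 10% removal and 83% at 20%, against 91% if the effect persists.

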## 11.0 Provisions to Monitor the Data to Ensure the Safety of Subjects

Safety will be monitored throughout the study based on the monitoring of adverse events, via electronic data collection. The period of observation for collection of non-serious adverse events extends from the time the subject gives informed consent until the completion of the End-of-Study visit or Early Termination Visit. Serious adverse events (SAE) will be reported to the MUSC IRB and to the sponsor from the time of informed consent through 30 days after the last use of the SinuSonic. Adverse event data listings will be reviewed by Principal Investigator and the research team at regular intervals throughout the study.

Safety data listings will be reviewed by Principal Investigator, Co-Investigators, and the research team at regular intervals throughout the study.

Safety will be monitored throughout the study based on monitoring of adverse events, and through collection of symptoms electronically. Collection of symptoms will occur via the Daily URI Symptoms Score questionnaires that are electronically sent to the consented patients.

The period of observation for collection of non-serious adverse events extends from the time the subject gives informed consent until completion of the End-of-study visit or Early Termination Visit. Serious adverse events (SAE) will be reported to the IRB and to the sponsor from the time of informed consent through 30 days after the last use of the SinuSonic. Adverse event data listings will be reviewed by the principal investigator, co-investigators, and the research team at regular intervals throughout the study.

All AEs, regardless of seriousness or relationship to SinuSonic use, spanning from the signature of the informed consent form until the end of the study as defined by the protocol for that patient, are to be reported to the Healthy Humming, LLC. All AEs which follow the IRB qualifications will also be reported to the IRB within 24 hours of site knowledge of the event.

The Investigator will take appropriate measures to follow all AEs until clinical recovery is complete and laboratory results have returned to normal, or until progression has been stabilized, or until death, in order to ensure the safety of the patients. This may imply that observations will continue beyond the last timepoint per protocol, and that additional investigations may be requested by the monitoring team up to as noticed by Healthy Humming, LLC.

In the case of occurrence of an SAE, the Investigator will immediately (within 24 hours) report the event to Healthy Humming, LLC and to the IRB, as applicable.

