#### **6.0 Setting**

Research will be conducted at geographical locations in the Southeast (SC, NC, GA, VA) that have similar fall viral URI seasons. Potential participant screening for all subjects across all aims, as well as informed consent and baseline evaluations, will occur remotely to avoid any risk to research personnel. All baseline and follow-up measures will be collected remotely using REDCap at 4 and 8 weeks.

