## **16.0 Payment**

For participating in this study, participants will be given a free device, but no payment will be given.

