## **18.0 Data safety monitoring and reporting**

Patients will initially be screened over the phone and informed consent obtained. This will occur during the summer months so we have a group of 300 subjects who pass this initial screen. Towards the end of the screening period, we will re-contact patients to confirm their interest in participation. As described above, we will also ask symptom scores to ensure TSS<9 and patient does not have an active URI at the start of the study.

If patients still wish to participate and still meet inclusion criteria, they will be randomized and devices shipped out within a week.

Safety will be monitored throughout the study based upon self reporting of symptoms. Subjects will be advised to seek medical care if at any time their symptoms become severe. Review of the daily reports will occur weekly to ensure the condition of each patient is adequately monitored for possible signs of URI or COVID19.

The period of observation for collection of non-serious adverse events extends from the time the subject gives informed consent until completion of the End-of-study visit or Early Termination Visit. Serious adverse events (SAE) will be reported from the time of informed consent through 30 days after the last use of the SinuSonic. Adverse event data listings will be reviewed at regular intervals throughout the study. In addition, investigators will be alerted of Adverse Events of interest via automated emails programmed in the EDC system. Patient compliance will be assessed via weekly phone calls from study coordinator.

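### No contact is scheduled in the 30-day SAE tail after last device use, and Section 12 stops data collection on investigator removal with no safety exception

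*Combined protocol and SAP*

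**What the plan says.** **Safety windows.** Section 11.0 sets SAE reporting "from the time of informed consent through 30 days after the last use of the SinuSonic", and Section 18.0 repeats it: "Serious adverse events (SAE) will be reported from the time of informed consent through 30 days after the last use of the SinuSonic". Non-serious events are collected "until the completion of the End-of-Study visit or Early Termination Visit". A later paragraph of Section 11.0 has all adverse events, whatever their seriousness, reported to the device company "until the end of the study as defined by the protocol for that patient". The same section asks the investigator to follow every adverse event to recovery, stabilisation or death, if need be past the last protocol time point, and to report any SAE within 24 hours.

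**Scheduled contact.** Section 3.0 states "The study duration is 8 weeks". Section 6.0 states "All baseline and follow-up measures will be collected remotely using REDCap at 4 and 8 weeks". The last column of Section 9.1 is the study endpoint at 60 days, and it is the only column with safety questions. Section 18.0 adds weekly review of the diaries and weekly compliance calls; neither is described as continuing after the endpoint. The Week 8 form in the Appendix asks about pain, bleeding and satisfaction, and has no SAE item.

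**Removal and device.** Where the investigator ends participation, Section 12 says "Subject will no longer be in the study and data will no longer be collected", without a safety exception. The paragraph of Section 12 on voluntary withdrawal does not address data collection. Section 16.0 says "participants will be given a free device, but no payment will be given". No return of the device is described.

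**The concern.** The plan defines an observation window for SAEs but gives no means of asking about events in its last 30 days. The study is fully remote, with no in-person visits (Section 8.0), so no later visit would bring an event to light. If the report says that SAEs were collected to 30 days after last use, an absence of events in the tail cannot be told apart from an absence of enquiry.

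Two further points are contradictions in the text. For a subject removed by the investigator, site staff cannot both stop collecting data and keep the SAE window and adverse event follow-up running. And an SAE that occurs a week or two after the endpoint lies inside one Section 11.0 period and outside the other.

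**Working it through.** The plan has no calculated figure to reproduce here. The check is day arithmetic, then a comparison of texts.

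**Inputs.** Window length after last use: 30 days (Sections 11.0 and 18.0). Study start: Day 12. Last scheduled contact: C = Day 60 (both Section 9.1). Treatment: 8 weeks = 56 days (Section 3.0).

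**Formulas.** With last use on day L, the window closes on W = L + 30. Days of the window beyond the last scheduled contact: U = max(0, W − C).

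| Case | L | W = L + 30 | U = max(0, W − 60) |
|---|---|---|---|
| Completer, last use at the endpoint column | 60 | 90 | 30 |
| Completer, 56 days of use counted from Day 12 | 12 + 56 − 1 = 67 | 97 | 37 |
| Stops at end of treatment week 4, stays in follow-up | 12 + 28 − 1 = 39 | 69 | 9 |
| Stops at end of treatment week 2, stays in follow-up | 12 + 14 − 1 = 25 | 55 | 0 |

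The first two rows differ because Section 9.1 allows 60 − 12 = 48 days from start to endpoint, not 56, if both days are counted from the same origin. If diaries run as long as use does, the last contact in the second row is Day 67 rather than Day 60, and the gap is again 97 − 67 = 30 days. So a completer has the whole 30-day tail without scheduled contact, while someone who stops early but keeps answering may be fully covered.

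**Removal by the investigator.** If data collection stops on day R and last use was on day L ≤ R, the part of the SAE window that falls after the stop is max(0, L + 30 − R), which is 30 days when use and removal fall on the same day. Section 12 names lost eligibility as one possible reason. The exclusion criteria in Section 4.0 include current nasal crusting and recent severe nosebleed, and Section 13.0 lists crusting and nosebleeds as device risks. The text therefore permits removal of a subject who has a listed device risk, although it does not say how often, if ever, this would happen. Section 11.0 refers to an Early Termination Visit, but Section 9.1 does not list one.

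**Two end dates.** If the study ends for a patient on the day of last use, the SAE window and the period of reporting to the device company differ by 30 days for serious events. Nothing in Section 11.0 says which governs.

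**The case against.** The strongest reply is that Sections 11.0 and 18.0 impose a duty to report, not a promise of active surveillance. The 24-hour SAE rule has no end date, and Section 11.0 expressly allows observation past the last time point, though only for events already known. This stands. A reader might infer that the 30-day window cannot be delivered at all; the documents do not support that, because SAEs that subjects volunteer can still be reported. The consent pages are not available and may tell subjects to report SAEs themselves. Capture would still be passive, and the conflict with Section 12 would remain.

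Other stronger readings also fail:

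- **Subjects who leave because of a problem are the most likely to be missed.** The stop on data collection is in the investigator-removal paragraph only. Voluntary withdrawal carries no such stop, and Sections 11.0 and 18.0 mention an Early Termination Visit.
- **The free device leaves the 30-day clock without a start.** Continued use after Week 8 is only a possibility, since the documents are silent on return and on later use. The daily diary asks for the number of uses, so last use within the study can be dated.
- **A given share of SAEs would fall in the gap.** That needs a constant SAE rate, including after use stops, and a denominator that includes the period from consent to study start. The documents give no SAE rate.

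It is also fair that this is a pilot of a legally marketed device, that Section 13.0 cites mild discomfort in 2.5–5% of patients with no bleeding or crusting, that safety data are only summarised (Section 10.0), and that the efficacy outcomes are untouched. This limits the weight of the point. On the end dates, the specific SAE sentence could be read as overriding the general one, but Section 11.0 does not say so.

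**Conclusion.** The point holds as a gap in how SAEs are ascertained, together with two contradictions that must be reconciled. For a completer, about 30 days of the plan's own SAE window have no scheduled contact (37 days past the Day 60 column on one reading of the schedule), so capture there depends on subjects or others volunteering events. For a subject removed by the investigator, Section 12 taken literally ends data collection while up to 30 days of the window are still open. For serious events, Section 11.0 gives two end dates up to 30 days apart if the study ends at last use.

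This assumes that diaries and weekly calls stop with the 8-week study, as their description suggests, and that no later contact is set out in the pages that are not available. That capture would be incomplete is a judgement about passive reporting in a remote study; how many SAEs would be missed cannot be worked out. The change should be made because it is cheap and improves the safety data, but the efficacy analysis does not depend on it.

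**What to change.** 1. **Section 9.1:** add one automated REDCap question on SAEs, sent to every randomised subject who has not refused further contact, 30 days after the last scheduled study use, or after the last diary-reported use for those who stop or leave early.
2. **Sections 11.0 and 18.0:** state that the 30 days are counted from that dated last study use. This makes the window determinate. For anyone who chose to go on using the device, it also ends sooner than the present wording implies, so the choice should be explicit.
3. **Section 12:** exempt SAE collection and follow-up of open adverse events from the stop on data collection.
4. **Section 11.0:** reconcile the two end dates for serious events, so that reporting to the device company and the SAE window agree. Reconcile the 48-day and 56-day readings of the schedule at the same time, because the anchor date depends on them.

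The cost is a short amendment and one extra automated survey. Some subjects will not respond, so the report should give the number who answered, by arm. Database closure moves back by about 30 days.
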